3.8.4 Data Analysis

Data to be analyzed for this study component will be obtained from routine HIV surveillance data as well as from the participating sites. Participating sites will maintain tracking logs, both for coupons provided to HIV-positive individuals at the test sites and for FI disbursement at the care sites. Information from the tracking logs, with all participant-identifying information removed, will be provided to the study team.

The analysis approach for testing the effectiveness of an FI intervention to link HIVpositive individuals from HIV test sites to HIV care sites compared to the SOC is described below. Analysis of secondary endpoints will be detailed in the statistical analysis plan.

3.8.4.1 Primary Effectiveness Analysis

The population for assessment of Linkage-to-Care is the following:

- 1. All individuals with newly detected HIV infections reported to the HIV surveillance system for the DOH jurisdiction of Washington, D.C. and the Bronx, NY who were tested at any of the 40 testing sites in the study
- 2. All participants eligible for re-linkage to care, defined as a WB recorded in the enhanced HIV/AIDS Reporting System (eHARs), at any of the 40 testing sites in the study after the implementation of FIs, who had no VL or CD4 assessment by a provider in the previous 12 months

The endpoint is the percentage of participants with a VL or CD4 cell count assessment within three months of the WB confirmation (separate from clinical assessment done at the time of the confirmation visit). Participants in the FI arm are attributed to the linkage-to-care strategy in place at the site where the first HIV-positive result was detected.

The estimation of intervention effect will test for a change in odds ratio of linkage-to-care between the SOC and FI test sites, assuming a correlation within participants tested at the same site, using Generalized Estimating Equations (GEE) methods.

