HIV care in Washington, D.C. is supported by a range of funding sources, to ensure that every individual in need of HIV treatment is provided both primary care and the supportive services necessary to remain in care. HAHSTA directly supports primary medical care programs at nine organizations in Washington, D.C. These primary medical care programs serve as a hub for services, with the responsibility of coordinating the services needed by their clients. In 2008 HAHSTA began implementing a best practice, four Rs (recruitment, recapture, retaining and results) approach to improving the continuum and continuity of HIV care in Washington, D.C. Recruitment or rapid entry to care links individuals who receive a positive HIV test immediately into primary care facilities, and includes special programs, such as: 1) Red Carpet Entry to Care services; 2) adult and adolescent healthcare navigation services; and 3) Rapid Entry to Care initiatives. To recapture patients into care, HAHSTA partnered with several funded care providers over three months to bring back into care nearly 900 people known to be living with HIV but found to not have had a CD4 cell count or VL test in the previous six months. For example, Family Medical Counseling Services re-established care with approximately 70% of 450 clients identified as lost to care, often after more than 10 contacts. Finally, retaining people living with HIV into care and ensuring quality results is a critical component of ensuring the continuity and continuum of care. HAHSTA has supported best-practice, outcome-based management of HIV-positive clients in care with affiliated primary care providers. HAHSTA has partnered with funded providers to use E-clinical Works and other electronic medical record (EMR) systems to institute evidence-based best practices such as deploying coordinated care teams, using focused, comprehensive health messaging, and identifying outcomes at every clinical encounter, with the goals of reducing missed medical appointments, increasing efficiency, increasing prophylaxis and increasing viral suppression.

Another specific strategy to increase linkage-to-care in Washington, D.C. is the requirement that all individuals with preliminary positive rapid HIV tests be linked immediately into care. When confirmatory testing is needed, it is performed at the initial medical visit, along with CD4 cell count, VL and other routine tests for HIV-positive individuals.

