3.2 Design for Linkage-to-Care

The Linkage-to-Care component of the study is a two-arm, site-randomized, prospective, effectiveness clinical trial conducted within each intervention community. This study component compares the effectiveness of an FI intervention to link HIV-positive individuals from HIV test sites to HIV care sites with the usual SOC procedures. Each HIV test site will be randomized to either the intervention or SOC arm of the study. For this component of the study, study outcomes will be evaluated through routinely reported HIV surveillance data. Using surveillance data, study outcomes will continue to be evaluated for a period of one year after the FI intervention ends.

In order to identify the SOC for linkage, against which the incentives intervention will be assessed, an appropriate facility administrator will complete a brief survey that will collect key attributes of HIV testing sites, including types of navigation and support services already available to patients to facilitate linkage-to-care. Data will be collected from sites annually from 2009 - 2013.

For the purposes of this protocol, we consider an HIV-positive individual linked to care when that person has a VL or CD4 cell count assessment at an HIV care site within 3 months of confirmatory WB testing.

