3.8.1.2 Endpoints for the Effectiveness of Linkage-to-Care

In this site-randomized design, Linkage-to-Care effectiveness endpoints will be evaluated for each site and intervention effectiveness assessed by comparing site outcomes for intervention vs. SOC sites.

The effectiveness endpoints for the Linkage-to-Care component of the study will be ascertained based on HIV surveillance data and will include the following:

- Proportion of HIV-positive individuals at each testing site, who either have a newly detected HIV infection (based on new surveillance case with confirmed WB) or who were previously diagnosed but were out of care (based on no VL or CD4 ascertainment in the year prior to a repeat WB test in an existing surveillance case), and who presently are linked to care as evidenced by having a CD4 cell count and/or VL measurement at a separate visit within three months of WB confirmation
- Mean time interval at each testing site from HIV diagnosis (WB confirmation) to first CD4 cell count or VL for those with newly detected HIV infection and those who were previously diagnosed but were out of care
- Proportion of HIV-positive individuals at a testing site (overall, and separately for those with newly detected HIV infection and those previously diagnosed who were out of care) with at least two CD4 cell count and VL measurements in the prior year

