3.8.2 Sample Size and Power

The primary endpoint of this study component is proportion of cases (newly diagnosed and previously diagnosed but not in care) with a CD4 cell count and/or VL measurement within three months of the diagnostic WB.

Randomization is by testing site, with balance achieved for baseline volume of testing and baseline linkage-to-care rates. Accrual of participants into the Linkage-to-Care

component of the study will occur over the first 24 months of the study, when eligible persons receive the FI coupon at an HIV test site randomized to the FI arm of the study. There will be no follow-up for this component of the study, other than the two visits in care (or a combined lab/provider intake visit).

In 2007, in the 20 testing sites with the highest volume in the Bronx, NY, 611 newly diagnosed HIV-infected people were identified. Of those, 77% were liked to care within three months, with linkage at different testing sites ranging from 30% to 100%. The mean number of newly diagnosed cases per provider in 2008 was 31, and ranged from five to 93. The intra-class correlation (ICC) of proportion linked to care in the Bronx was 0.27.

In 2008, in the 20 testing sites in Washington, D.C, the jurisdiction with the highest volume of people testing HIV-positive, 783 newly infected cases were identified. Of these, 67% were linked to care, ranging across different testing sites from 5% to 100%. The mean number of newly diagnosed cases per provider in 2008 was 40, and ranged from eight to 143. The ICC of proportion linked was 0.31.

These estimates do not include the population of those re-linking to care. It is anticipated that linkage success in SOC for this population will be lower because of the history of loss to care. We could reasonably expect that: 1) the number of people eligible for linkage-to-care will be higher because of longer study duration and addition of re-linked to care cases; 2) the proportion linked to care will be lower because of the re-linked to care cases; and, therefore, 3) the ICC will be smaller. It is assumed that the number of cases to be linked to care during the 24-month study duration will be similar to these past case loads on an annual basis. We will randomize 20 testing sites in each intervention city, and we expect to identify between 1200 and 2400 individuals for linkage-to-care, a mean of 60-120 people per testing site.

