7.1 HIV Testing Data

HIV testing data will be used to select HIV test sites for randomization to the intervention vs. SOC arm, and as a process measure for the testing intervention in ED and inpatient facilities (Table 5). For selection of HIV test sites for interventions, information on HIV testing is available for HIV test sites that are publicly supported through federal funds in each of the six communities included in this study; additional data are available for other

HIV test sites supported in some local jurisdictions, such as NYC's AIDS Institute Reporting System. This includes the majority of HIV testing conducted by CBOs.

Data Sources and Definitions						
Information needed Description		Data source	Variables			
HIV Testing Data						
Site selection, intervention communities						
Volume of testing	Number of persons tested in XX year, by testing site	Local PEMS, local testing data	Name of testing facility, testing date			
	Number of new diagnoses, by testing site	HIV surveillance data	Name of facility of diagnosis, date of diagnosis			
	Where available, number of case reports to surveillance, by testing site	HIV surveillance data	Name of facility of diagnosis, date of diagnosis			
Process mea	sures for HIV testing interven	tions, intervention (communities			
Number of persons eligible	Number of persons eligible	Project specific collection at intervention sites	Data may or may not already be collected at selected sites. If not collected, collection will be implemented for this study			
Number of persons tested	Number of persons tested	Project specific collection at intervention sites	Data may or may not already be collected at selected sites. If not collected, collection will be implemented for this study			
Number of new diagnoses	Number of new diagnoses	HIV surveillance data, and project specific collection at intervention sites	Surveillance data: name of testing facility, testing data. Data may or may not be collected by selected sites, and if not collected, can be implemented at site or use surveillance data.			
	HIV Surveillance	e Data				
	Outcome Meas	ures				
Number/proportion of persons newly diagnosed who entered care, by site CD4 or VL within 3 months of diagnosis (CD4/VL date not equal to diagnosis date), by site		HIV surveillance data	HIV diagnosis date, name of testing site, VL date, VL result, CD4 date, CD4 result, demographics (DOB, sex, race/ethnicity, transmission category)			

 Table 5.
 Data Sources and Definitions

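### The primary linkage endpoint is defined in conflicting ways, and the stricter wording can score D.C. patients who reach care as not linked when the Western blot, CD4 and viral load are drawn together at the first care visit

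*Protocol*

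**What the plan says.** The protocol defines linkage in several places.

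- Section 3.2 (Design) treats a person as linked who "has a VL or CD4 cell count assessment at an HIV care site within 3 months of confirmatory WB testing".
- Section 3.8.2 (Sample Size and Power) gives the primary endpoint as the proportion of cases "with a CD4 cell count and/or VL measurement within three months of the diagnostic WB".
- Section 3.8.1.2 (Endpoints) requires "having a CD4 cell count and/or VL measurement at a separate visit within three months of WB confirmation".
- Section 3.8.4.1 (Primary Effectiveness Analysis) requires the result to be "separate from clinical assessment done at the time of the confirmation visit".
- Table 5 in Section 7.1, in the row for newly diagnosed persons, adds "CD4/VL date not equal to diagnosis date".

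On the D.C. care pathway, Section 1.1.3.3 requires everyone with a preliminary positive rapid test to be linked to care at once and adds: "When confirmatory testing is needed, it is performed at the initial medical visit, along with CD4 cell count, VL and other routine tests".

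Section 3.5 pays $25 for the blood draw at the care site and $100 for the provider interaction, or $125 when one visit covers both. No repeat laboratory test is required. Section 3.8.4.1 says that participants in the FI arm are "attributed to the linkage-to-care strategy in place at the site where the first HIV-positive result was detected". It states no matching rule for the SOC arm.

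**The concern.** The separate-visit condition makes sense for laboratory work drawn at the test site at diagnosis, for example in an emergency department, because such a draw shows nothing about reaching care. The text does not limit the condition to that case. Where the WB is itself drawn at the care site, the confirmation visit is the first care visit, and the condition removes the very event the endpoint is meant to detect. A patient could complete one comprehensive care visit, receive the full $125 and still be scored as not linked.

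At stake is the primary comparison in the city that has 20 of the 40 test sites. For the affected patients the endpoint would measure whether a second CD4 or viral load was ordered within three months, not whether they reached care. Section 4.8.1.2 describes viral loads as ordered roughly quarterly, so the next routine result would fall near the edge of the window.

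**Working it through.** **Step 1: the definitions side by side.**

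| Place | Visit or date condition | Facility condition |
|---|---|---|
| 3.2 | none | HIV care site |
| 3.8.2 | none | none |
| 3.8.1.2 | separate visit | none |
| 3.8.4.1 | not the confirmation visit | none |
| Table 5, newly diagnosed | date differs from diagnosis date | none |
| Table 5, previously diagnosed | none | none |

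**Step 2: two test cases.**

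*Case A.* A newly diagnosed D.C. patient has a reactive rapid test at a study test site and attends a care site, where WB, CD4 and viral load are drawn together. No further CD4 or viral load follows within three months. The patient is linked under 3.2 and 3.8.2. The patient is not linked under 3.8.1.2, 3.8.4.1 and Table 5 (taking the WB date as the diagnosis date).

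*Case B.* A patient is confirmed at a test site that is not an HIV care site, has a CD4 drawn there the same day, and never goes to care. The patient is linked under 3.8.2 and not linked under the others.

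Only 3.2, the one definition with a facility condition, classifies both cases sensibly.

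**Step 3: size if the exclusion applies.** No stated figure is in dispute, so there is none to reproduce. Inputs: 67% (SOC) versus 80% (FI), from Table 2 in Section 3.8.2, taken here as true D.C. linkage rates. Let f be the share of linked D.C. patients whose only CD4 or viral load in the window comes from the WB visit. The documents do not give f, so a range is shown.

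Observed rate = true rate × (1 − f). With f equal by arm, observed difference = 13 × (1 − f).

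| f | SOC | FI | D.C. difference | Both cities |
|---|---|---|---|---|
| 0 | 67.0% | 80.0% | 13.0 | 13.0 |
| 0.10 | 60.3% | 72.0% | 11.7 | 12.4 |
| 0.25 | 50.3% | 60.0% | 9.8 | 11.4 |
| 0.50 | 33.5% | 40.0% | 6.5 | 9.8 |

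The last column is [13 + 13 × (1 − f)] / 2. It assumes equal city weights and an unaffected Bronx.

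**Step 4: unequal f.** With f = 0.25 in SOC and 0.50 in FI, the rates become 67 × 0.75 = 50.3% and 80 × 0.50 = 40.0%. The sign reverses.

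**Step 5: the denominator.** Suppose instead that half of the unlinked D.C. patients never have a WB and leave the analysis. SOC becomes 67 / (67 + 33 × 0.5) = 80.2% and FI becomes 80 / (80 + 20 × 0.5) = 88.9%. Both rates rise and the difference falls to 8.6 points.

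**The case against.** Much can be said on the other side, and most of it limits the size of the problem.

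- A later CD4 or viral load within three months still counts, so not every such linkage is lost. Patients confirmed at the test site are unaffected.
- Section 1.1.3.3 is background on city policy and applies only where confirmation is still needed. About seven of the 20 test sites per city are hospitals (3.6.3). In D.C., admission testing is to be added to standing blood work (2.6.3.2), and the rapid-test pathway is not shown to cover it.
- The blood draw alone earns $25 of the $125. The larger payment usually falls at a second visit.
- The separate-visit rule has a sound purpose (Case B).

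A reader might infer that D.C. preliminary positives who never attend care cannot enter surveillance or the denominator. The documents do not support this. Section 3.8.2 reports 783 D.C. cases in 2008 assigned to 20 testing sites with 67% linked, so about 783 × 0.33 = 258 unlinked people were recorded and attributed. Section 7.2 also lists other routes into surveillance, such as positive EIA, detectable viral load and provider reports. Some loss is possible, but its extent is unknown.

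A reader might also infer that the effect must be biased toward zero and the D.C. rate understated. That does not follow. The exclusion lowers the observed rate and loss from the denominator raises it, and Step 4 shows that unequal f can reverse the sign.

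The contradiction itself stands, as does the absence of any rule for the D.C. pathway. It cannot be left to the analysis plan: Section 3.8.4 defers secondary endpoints, and the primary endpoint is fixed here.

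**Conclusion.** The primary linkage endpoint is internally inconsistent, and under the wording of the analysis section some truly linked D.C. patients can be scored as failures. It needs one definition before outcome data are analysed.

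The size is conditional. With f equal by arm, a 13-point D.C. difference shrinks to 11.7, 9.8 or 6.5 points at f = 0.10, 0.25 or 0.50. These figures assume that 67% and 80% are true linkage rates. Section 3.8.2 does not say whether the 67% baseline already excluded same-visit results. If it did, f in 2008 could not have exceeded 1 − 0.67 = 0.33, since the true rate cannot exceed 100%. If f differs by arm, or unlinked patients lack a WB, the direction of bias is not predictable.

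Attribution needs the same repair. The stated rule names only the FI arm, and the re-linkage group is defined by a WB recorded at a study testing site, so on a literal reading a WB drawn at a care site falls outside it. For newly detected cases, the site assigned depends on which facility surveillance records.

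**What to change.** Reconcile Sections 3.2, 3.8.1.2, 3.8.2, 3.8.4.1 and Table 5 to one facility-based rule for both arms:

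- Linked means a CD4 or viral load ordered by an HIV care site within three months of the WB, including one on the WB date.
- A same-date CD4 or viral load ordered by the test site, including its emergency department or inpatient unit, does not count.
- Participants in both arms are attributed to the study test site where the in-study positive test was done, including when the WB is drawn at a care site.
- The separate-date definition is reported as a sensitivity analysis.

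The cost is endpoint wording, programming and ordering-facility codes on laboratory records. The viral suppression endpoint already relies on the ordering site (Section 4.8.1.2; Table 5 lists the treatment site), so this is a modest demand. The weak point is hospitals with a co-located HIV clinic: they need a unit-level code or must be handled in the sensitivity analysis.

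Starting the clock at the reactive rapid test, or using preliminary positives as the denominator, is not proposed. Table 6 lists no reactive rapid result, and Section 3.9 limits individual data to what the surveillance databases hold.

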3.4 Study Sites for Linkage-to-Care

Twenty HIV test sites will be selected from Washington, D.C. and 20 HIV test sites will be selected from the Bronx to participate in the Linkage-to-Care component of this study.

HIV test sites will be selected based on two primary criteria: 1) site agreement to participate in this component of the study, and 2) sites with the highest volume of HIV-positive individuals identified in the previous year. Additional site selection criteria may be considered if a total of 40 HIV test sites cannot be chosen based on the primary criteria.

In each community, these 20 sites will be randomized such that 10 will use the FI intervention, described in Section 3.5, to link HIV-patients to care and 10 will use the SOC only.

The site randomization will be balanced by the following two baseline characteristics:

- The number of HIV-positive individuals identified in the previous year
- The rate of linkage-to-care within three months of HIV diagnosis over the course of the calendar year prior to study initiation

In addition, 20 care sites will be selected in Washington, D.C. and 20 care sites will be selected in the Bronx, NY. These care sites will redeem the coupons provided to patients by the test sites selected for the FI arm.

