Table 2 below gives the mean number of linkage cases needed per testing site to detect an increase in linkage-to-care given 20 sites per arm (*i.e.* 40 in all). With a mean ranging from 80 to 100 linkages per site during the 24 months of the study, we would have 80% power, even with a high ICC, to detect a 13% change in proportion linked to care. If higher numbers are eligible for intervention due to linkage-to-care (*e.g.* 140), we would attain 90% power to detect this magnitude of difference. Note that the ICC coefficient estimated from the linkage-to-care of newly detected cases is high in large part because of sites with a small number of newly detected cases and 100% success in linking to care. It is probable that the ICC observed in the trial will be lower.

This sample size calculation for clustered designs uses the approach described by Thomson, Hayes and Cousens (Hayes and Bennett 1999; Thomson, Hayes et al. 2009).

 Table 2.
 Mean number at each site required to achieve sufficient power to detect differences in proportion of newly detected or reconnected to care within three months of testing. Number of clusters fixed at 20 per arm

Mean percentage linked to care at a site		Standard deviation can	-	Intra-class	Mean number of potential cases for linkage-to-care per testing site	
Standard of care	Intervention	Standard of care	Intervention	correlation	80% power	90% power
67%	80%	17%	12%	0.127	37	49
67%	80%	20%	15%	0.183	54	72
67%	80%	26%	19%	0.309	102	137
67%	75%	17%	14%	0.127	105	140
67%	75%	20%	17%	0.183	152	203
67%	75%	26%	22%	0.309	287	384

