3.8.3 Randomization Scheme

In the Linkage-to-Care study component, HIV testing sites will be randomized to use FIs or the SOC.

HIV test sites will be assigned to one of the following two arms:

- An arm offering FIs: Test sites assigned to this arm will provide coupons to all individuals testing HIV-positive, who are not already linked to HIV care. The coupons can be redeemed for the FI at a participating HIV care site.
- An arm continuing with SOC: Each person who tests HIV-positive, and is not currently in care, will be directed to HIV care sites using the site's SOC procedures.

The site randomization will be balanced by the following two baseline characteristics:

- The number of HIV-positive individuals identified in the previous year
- The rate of linkage-to-care within three months of HIV diagnosis over the course of the calendar year prior to study initiation

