4.0 VIRAL SUPPRESSION

4.1 Study Objectives for Viral Suppression

The **primary feasibility objectives** for using FIs to incentivize HIV-positive patients to achieve and maintain viral suppression (HIV RNA < 400 copies/mL) will be measured by determining the following:

- Proportion and number of patients in care, on ART (eligible for incentives), and receiving incentives upon achieving VL suppression
- Number of incentives disbursed compared with the total number of incentives available to eligible patients over the study duration [measurement of duration of viral suppression]
- Overall cost of program including staffing, infrastructure and incentives
- Number of patients previously adherent to ART who change from non-intervention to intervention care sites

In order to monitor the implementation of the FI program, certain parameters will be gathered from a subset of participating sites at various time points to ensure program quality. These parameters will include: the proportion and number of patients in care, on ART (eligible for incentives) and receiving incentives, as well as the incentive amount received compared with the total number on ART who would be eligible.

The **primary effectiveness objective** is to compare an FI intervention with the SOC for achieving and maintaining suppressed VL in HIV-positive patients in care, managed under the prevailing guidelines for the initiation of ART. For sites in each intervention arm, this objective will be measured by the following:

- Comparing the mean proportion of patients in care at a site who have suppressed VL (HIV RNA <400 copies/mL) during the fixed 12-month calendar evaluation period beginning 12 months after initiation of the FIs at that site
- Comparing the trend in mean proportion of patients in care at a site who have suppressed VL over time since initiation of FIs

• Comparing the mean proportion of patients who have suppressed VL (HIV RNA <400 copies/mL) after cessation of incentives

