4.4 Study Sites for Viral Suppression

Twenty HIV care sites will be selected from Washington, D.C. and 20 HIV care sites will be selected from the Bronx to participate in this component of the study. Sites will be selected based on two primary criteria: 1) site agreement to participate in this component of the study, and 2) sites with the highest number of HIV-positive patients in care in the previous year. Additional site selection criteria may be considered if a total of 40 HIV care sites cannot be chosen based on the primary criteria.

HIV care sites will be randomized 1:1 to the FI vs. SOC, stratified by city and balanced by size of patient population in a clinic and baseline levels of proportion of VL showing suppression. In each city, these 20 sites will be randomized such that 10 will use the FI intervention, described in Section 4.5, to promote viral suppression in HIV-patients on ART and 10 will continue the existing SOC.

The site randomization will be balanced by the following two baseline characteristics:

• The size of the site's HIV-positive patient case load

• The proportion of HIV-positive patients with VL suppression at each site

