4.8.4.1 Primary Effectiveness Analysis

The assessment cohort includes all HIV cases identified from HIV surveillance in the intervention city DOH jurisdiction that have a VL assessment in the 24 months of trial duration. The assessment period for each site begins 12 months after the onset of FIs in each city. An intention-to-treat approach will be used to assign patients to the care site assignment existing at the trial onset. For the 12-month assessment period (*i.e.* from 12 through 24 months), all VLs in the surveillance data assessed by the 40 clinics in the study are used to assess differences in percent achieving viral suppression by study arm. Details about each site's contribution of patients who enter into care during the study will be provided in the statistical analysis plan. As described in 4.8.1.2, an imputation scheme for assessing VL suppression during the 12 months of the assessment that avoids the bias of missing assessments will be applied to all patients in care.
The estimate of intervention effect is the odds ratio of VL suppression in the FI intervention compared to SOC arms, assuming both a within-person and within-clinic correlation, stratified by city, using GEE methods. Sensitivity analysis will be conducted to assess the impact of patients who switch providers or establish care at multiple providers during the trial.

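### Both cluster-randomised primary GEE models leave out the baseline site rate and site size on which randomisation is balanced (and, for linkage, city); if site rates persist over time, this costs power

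*Protocol*

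**What the plan says.** **Linkage-to-Care.** Section 3.4 randomises test sites within city: "In each community, these 20 sites will be randomized such that 10 will use the FI intervention", the other 10 staying on standard of care. Sections 3.4 and 3.8.3 balance the allocation on two site characteristics: "The number of HIV-positive individuals identified in the previous year" and "The rate of linkage-to-care within three months of HIV diagnosis over the course of the calendar year prior to study initiation". Section 3.8.4.1 gives the primary analysis as an odds ratio between arms, "assuming a correlation within participants tested at the same site, using Generalized Estimating Equations (GEE) methods". It names no city term, baseline rate or site volume.

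**Viral Suppression.** Section 4.4 has care sites "stratified by city and balanced by size of patient population in a clinic and baseline levels of proportion of VL showing suppression". Section 4.8.4.1 estimates an odds ratio "assuming both a within-person and within-clinic correlation, stratified by city, using GEE methods". City is there; clinic size and baseline suppression are not.

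Sections 3.8.4 and 4.8.4 both say that the effectiveness analysis is described in the text that follows, and leave the secondary endpoints to the SAP. For suppression, 4.8.1.2 and 4.8.4.1 also leave imputation, multiple sites of care and patients entering care to the SAP. Covariates are not among the items deferred.

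**The concern.** Balancing sites on a prognostic factor removes its contribution to the true variability of the arm difference. A model without that factor still counts its between-site variance in the standard error. The standard error is then too large for the design, the test rejects too rarely under the null, and power is lost.

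With the number of sites fixed ("Number of clusters fixed at 20 per arm"), this matters more than it would in an individually randomised trial: nearly all the uncertainty in a site proportion comes from differences between sites, so more patients per site help little. The two primary models also treat city differently although both randomisations are done within city.

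**Working it through.** **Inputs.** Site rates, SDs, ICCs and cluster sizes come from Tables 2 and 3 (sections 3.8.2 and 4.8.2), with 20 sites per arm. Two-sided 5% is assumed; the protocol states it only for Prevention for Positives (5.9.2). The site-level correlation r between baseline-year and trial-period rates is not in the documents and is shown as a range.

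**1. The plan's own power figure.** Section 3.8.2 states 80% power for 67% versus 80% with a mean of 80-100 cases per site at the high ICC. The Hayes-Bennett formula is

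V = [p0(1-p0) + p1(1-p1)]/m + s0² + s1²; power = Φ(√[(c-1)d²/V] - 1.96).

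At m = 100: V = 0.3811/100 + 0.26² + 0.19² = 0.0038 + 0.1037 = 0.1075. Power = Φ(√[19 × 0.13²/0.1075] - 1.96) = Φ(-0.23) = 41%. The 80% is not reproduced. That is a separate matter, but it makes precision more valuable.

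**2. Where the variance lies.** Between-site share of the variance of a site proportion = (s0² + s1²)/V:

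| Table row | Within, per site | Between | Share |
|---|---|---|---|
| Linkage 67/80, SD 17/12, m = 37 | 0.0103 | 0.0433 | 81% |
| Linkage 67/80, SD 26/19, m = 102 | 0.0037 | 0.1037 | 97% |
| Suppression 60/70, SD 15/13, m = 57 | 0.0079 | 0.0394 | 83% |
| Suppression 60/66, SD 15/14, m = 217 | 0.0021 | 0.0421 | 95% |

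**3. Type I error of the unadjusted test.** Under perfect balance on a site covariate with correlation r, α = 2[1 - Φ(1.96/√(1-r²))]. Two simulations with 40 sites allow for imperfect balance: a site-level normal model, and a logistic exchangeable GEE with an uncorrected sandwich z-test (constrained or paired allocation within city, about 35 baseline and 80 trial cases per site, 1,500 runs).

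| r | Formula | Site-level | GEE |
|---|---|---|---|
| 0 | 5.0% | – | 4.9-5.7% |
| 0.3 | 4.0% | 4.5% | 4.7-5.2% |
| 0.5 | 2.4% | 2.2% | 3.5-3.9% |
| 0.7 | 0.6% | 0.9% | 1.5-3.0% |

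**4. Power for 67% versus 80%, unadjusted to adjusted.** The adjusted GEE has city and baseline rate, with a corrected sandwich and t reference (800 runs).

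| r | Site-level, SD about 22.5% | GEE, control SD 26% | GEE, control SD 17% |
|---|---|---|---|
| 0.3 | 44% to 48% | 39% to 39-40% | 71% to 71-72% |
| 0.5 | 42% to 53% | 39-40% to 44-45% | 71-72% to 75-77% |
| 0.7 | 37% to 68% | 36-38% to 53-54% | 69-71% to 83% |

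**5. Adjustment without small-sample correction.** The same adjusted GEE with an uncorrected sandwich and z reference rejects 6.2-8.4% under the null; with the correction, 3.8-6.2%.

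**6. City alone.** Linkage is 77% in the Bronx and 67% in D.C. (3.8.2), a between-city variance of (0.10/2)² = 0.0025. That is 0.0025/0.17² = 9% to 0.0025/0.26² = 4% of between-site variance. Treating the share as r² in the step 3 formula gives α of 4.0% to 4.6%.

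**7. Could r be high?** The reliability of a one-year site rate is m·ICC/[1 + (m-1)·ICC]. For Bronx linkage (m = 31, ICC 0.27) it is 8.37/9.10 = 0.92; for D.C. (m = 40, ICC 0.31) it is 12.4/13.09 = 0.95. One year's rate measures that year's site level well, on average. Stability across years is undocumented.

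**The case against.** The text is silent on covariates; it does not forbid them. Covariate lists, working correlation and small-sample corrections are ordinary SAP content, and the SAP is not at hand. This stands in part: the SAP may already contain the terms. But both sections present the primary analysis as described there, and the suppression model does name city, so its omission for linkage, and that of the balancing variables in both, is worth correcting in the protocol text.

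The documents also give reasons to doubt a high r. The baseline linkage figures cover new diagnoses only, while the endpoint adds people re-entering care (3.8.2, 3.8.4.1). Some sites had as few as five or eight cases. D.C. linkage rose from about 50% to 67% between 2006 and 2007, on somewhat different laboratory evidence (1.1.3.3). D.C. baseline suppression uses the latest viral load among those assessed (4.8.2), whereas the endpoint is imputed by quarter (4.8.1.2). These points stand, and are why the size is given as a range.

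A reader might infer several stronger claims that the documents do not support:
- That the tests are severely conservative whatever the data. This needs a high r and tight balancing; neither is documented.
- That a few very large clinics (sizes run from 35 to 3,300) will make the suppression test over-reject badly. That needs an independence working model, which an analysis assuming within-clinic correlation does not naturally mean.
- That some 95% of all variance lies between sites. That is the share in a site's proportion; the share of total variance is the ICC, 0.07 to 0.31.
- That omitting city is costly. Step 6 shows it is minor.
- That adjustment is the only source of precision, or that Prevention for Positives has the same fault. Neither is shown; the latter is individually randomised.

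**Conclusion.** The point holds as a matter of efficiency. A conservative test still controls type I error, so validity is not at stake. Neither primary model names the baseline site rate or site size that its randomisation balances on, and the linkage model also omits city.

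The loss depends on r. At 0.3 or below, type I error is near 5% and adjustment gains little or nothing. At 0.5, type I error is about 2-4% and linkage power in the high-variance scenarios rises by about 5-11 points. At 0.7 the figures are about 1-3% and 15-30 points. With a control SD of 17% the gain at 0.7 is about 12-14 points. These results assume two-sided 5%, 40 sites and reasonably close balance on the baseline rate. Because between-site variance makes up roughly 81-97% of the variance of a site proportion in the rows checked, explaining it is the main analytic lever. It is worth doing, since the data are already needed for randomisation.

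**What to change.** In sections 3.8.4.1 and 4.8.4.1, keep the odds-ratio GEE and state:
- covariates: city, baseline-year site rate (linkage or suppression, as used for balancing) and log baseline site size;
- exchangeable within-site working correlation;
- bias-corrected sandwich variance with a t reference on about 35 degrees of freedom (40 sites less five coefficients: intercept, arm and three covariates).

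The correction should go in together with the covariates, since adjustment alone is liberal.

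An equal-weight regression of site proportions on arm and the same covariates can serve as a sensitivity analysis. It sits close to the objective in section 4.1, "Comparing the mean proportion of patients in care at a site who have suppressed VL", but gives a difference in proportions, so it should not replace the stated odds ratio.

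The cost is wording, about three degrees of freedom, an odds ratio that is conditional on the site covariates, and no gain if baseline rates turn out not to predict. No new data are needed.
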